#### 9.13 Study Arms.

Enhanced Usual Care. Current usual care includes variable physician prescribing and/or nurse counseling, and no active SMS or surveillance of medication use post-visits.

We are enhancing this usual care by adding UMS materials as a clinic standard, per Erie's request following their current experience with these materials. All patients at Erie or NMHC, thus all patients in this study, will begin to receive UMS-related tools at their primary care visit to support Rx use. These materials have previously been successfully piloted in multiple NIH-funded studies. These include:

1. *UMS Rx Instructions ('Sigs')*. The UMS is defined in Section 2.2. We have already successfully replaced existing EHR default sigs for 305 Rx drugs in primary care with UMS instructions [R21CA132771], and tested use of UMS sigs in pharmacy practice [R01HS017687, R01HS019435], in English and Spanish.
2. *MedSheets*. As an additional measure funded by AHRQ [R18HS17220], we created single-page, plain language Rx information sheets following health literacy best practices with content appropriately sequenced from a patient's perspective (drug name, indication, purpose/benefit, how to take, for how long, when to call your doctor, when to stop taking and call your doctor, important information). These sheets pull in the UMS sig to tailor content and serve as a tangible, 'patient-friendly' addition to the after-visit summary. Medsheets for a total of 305 Rx drugs have been embedded within the Epic EHR at NMFF and are automatically generated and distributed at check out to patients with new Rx prescriptions. Lexile analyses were performed on these sheets, confirming each to meet a < 8th grade readability standard. The content was developed by two pharmacists, performing an environmental scan of existing tools. Patients, physicians, and health literacy experts reviewed the material and guided revisions.
3. *MedList*. We re-designed the EHR medication list to impart the UMS to an entire Rx regimen (R18HS17220; U19HS021093). All medicines are listed and instructions consolidated in UMS form (requiring e-confirmation by doctor to ensure patient safety and flagged by clinical decision support tools if harmful interactions exist in regimen – supervised by [name]) to visually depict patients' morning, noon, evening, and bedtime medicine.

The UMS EHR tools have been piloted in Epic and Cerner, and are now being implemented in GE Centricity for this proposal now. Among 144 patients at the NMFF General Medicine clinic, nearly all (91%) patients received their MedList, UMS sigs, and MedSheets for new medications; 85% reviewed it with their doctor. Feedback from 20 physicians offered unanimous positive feedback on the tools. [R18HS17220].

**9.14 SMS Text Reminders.** For those patients receiving text reminders (SMS; SMS+Portal), daily text reminders will be sent post baseline following the UMS intervals. The texts will continue daily, with the option to opt out at any time. Stopping the texts will not impact their continuance in the study. Texts will automatically stop after 6 weeks, with an option at that time for patients to opt back in to the service. Those who opt back in will get the texts all 6 months of the study, or until they decide to stop. In past studies we have sent texts for one week, but recent studies have shown patients may benefit from longer text interventions. A covariate will be to look at the effect of length of text intervention to patient adherence, as well

as whether or not people opted out. Participants without unlimited texting plans will be reimbursed the total cost of receiving the texts. Patients will receive uniform, generic messages around UMS time intervals such as, “Good Morning! Please remember to take your medicines today.” and, “Hope you had a great day and remembered to take all your medicine!”

We will use EZ Texting, a safe, economical, premium Internet SMS text service plan, to program and schedule discrete UMS-centered text messages. These will be sent at standard intervals for all patients based on their regimen, with a maximum of two times a day (i.e. 1 or 2 times daily depending on regimen). Because these reminders are sent daily, we have limited the number of times sent per day so as not to burden and overwhelm the patient. Generic reminders are used due to the complexity of patient regimens and the SMS text message itself sent around the general time of behavior is a memory support. The premium plan ensures patients do not receive promotional messages with the text. A trained RC will orient and confirm patients can retrieve text messages. The RC will also instruct patients to abstain from reading text messages while driving and instead read messages and take medicines once they can safely concentrate on the task.

**9.15 EHR Web-Based Patient Portal.** The addition of the patient portal will provide opportunities to have ongoing communications with their clinic, real-time reconciliation and updating of medication lists, access to regimen-specific medication information, and to provide a feedback loop informing healthcare providers of adherence-related behaviors and concerns. The encrypted patient portal website will be managed by the Alliance HIT team and the MyChart team, under [name] supervision. Secured instant messaging and email features to communicate with clinic staff are already available within the portal. The additional build out above these informational and communication features will be a periodic requests for patients to (1) identify if they missed taking any of the medicine in their regimen in the past 3 days, and (2) list any concerns or problems related to refill, cost, side effects, or management of their medicines. This process has previously been piloted with patients and can be performed in three minutes or less. Patients in this arm will be asked to fill this survey out 2 weeks, 1, 2, 3, 4, and 5 months post baseline. An email will be sent to patients at these time points, requesting that they access the portal and complete the regimen adherence assessment (embedded in the portal). The information submitted back by the patient will be sent back to the EHR and directed to the responsible doctor or nurse. Identified ‘champions’ at Erie and NMHC will be trained to review the files and identify patients with regimen-related concerns. Patients who do not complete the assessment within 48 hours will be sent a second email reminder. If they still do not fill out the survey, a third and final reminder will be sent. Patients who self-report any concerns or who demonstrate incorrect or missed doses will also trigger nurse follow-up. The RC will create a MyChart or MyErieHealth account for patients that do not already have a patient portal account, depending on the clinic they attend. For Erie patients, a MyErieHealth account will be created through the MyErieHealth admin page. For Northwestern patients, the RC will obtain a MyChart activation code by accessing a patient's chart through Epic. Erie staff will send encrypted emails weekly or as needed to NU RC's with a list of patients that have completed the portal survey. For Northwestern patients, RC's will

determine if a survey was completed by accessing a patient's chart through Epic to see a record of a completed UMS Portal MyChart survey.

**9.16 Nurse Training.** Nurses will be educated on health literacy and health communication best practices, barriers to medication self-management, and how to briefly counsel patients via face-to-face and telephone using teach-to-goal and implementation intention approaches. Our team has used these techniques in prior studies that tested a low literacy diabetes education strategy in FQHCs. Patients at the time of enrollment will also be extensively oriented to the patient portal and use of the EHR and portal tools. The clinic nurse phone number and email will be provided for technical support.

**9.17 Pharmacy Release.**

To calculate PDC, we will need to collect pharmacy claims data for each patient that grants permission. For each patient, we will assess adherence within drug class. If a patient fills a prescription for a drug and switches to another drug within the same class, all prescriptions will be summed in the numerator. Once the patients have signed the informed consent, patients will be asked which pharmacies they use to fill their prescriptions. They will be asked to sign the appropriate release(s) allowing us to obtain fill information from pharmacies used during the study. We will request to obtain information for any medicine that was filled 6 months prior to baseline to 1 year post baseline. If the interview is completed over the phone, a pharmacy release form may be mailed to the participant to be filled out and returned to the study team.

★ **COVID-19 Waves 5-9 Pharmacy fill data.** For participants that complete COVID Wave 5-9, participants will be asked if they use Walgreens or CVS to fill their prescriptions. During the COVID consent process, participants will be informed that Walgreens and CVS Pharmacy may access, receive, or use their personal information, based on the pharmacies they utilize.

**9.18 Data Sources.** Data sources for this study will include in-person interviews or phone interview with participants (see attached surveys), blood pressure machine readings during in-person visits, Electronic Health Record chart review, and pharmacy data.

**9.19 Data Collection.** In order for the researchers to evaluate the intervention and how well it is being utilized, we will ask the Alliance to provide some data to Northwestern for Erie patients. For consented patients, the Alliance/Erie Family Health Center will provide data, including basic demographics, current medication lists and clinical outcomes from the patients' medical record. The Alliance/Erie Family Health Center will also provide the above detailed information in the form of de-identified, aggregate data (i.e. frequencies and means (SD) per arm) for all patients, regardless of whether or not the patient consented to participate in the study. All data will be transferred via secure Sharepoint site.

Specifically:

- Alliance will send contact information for identified eligible patients
  - Study ID
  - Patient's medical number

- Patient name
  - Clinic and provider name
  - Home and cell phone number
  - Address
  - Sex
  - Date of Birth
  - Primary language
  - Date of last primary doctor appointment at Erie
  - All drugs prescribed (name, dose, form, GPI, instruction, date prescribed, number of refills, pharmacy, quantity)
- NU will send Alliance/Erie Family Health Center Study IDs and baseline interview dates, linked by patient ID
- Alliance will send the following information to Northwestern for consented patients:
  - Study ID
  - All values 6 months prior to baseline & 12 months post
    - Blood pressure
    - HbA1c
    - Cholesterol levels
  - Information on all prescribed medicines baseline to 12 months post (name, dose, form, GPI, instruction, date prescribed, number of refills, pharmacy, quantity)
  - Current at baseline and 12 months post
    - Chronic conditions
    - COVID-19 diagnosis and/or results of antibody test
  - All clinic visits/appointments 6 months prior to baseline and 12 months post (date, provider, meds prescribed, visit type)
  - Patient portal survey results, date completed, and possible clinic contact for patients in either of the portal arms
  - Patient portal use 6 months prior to baseline and 36 months post baseline
    - how many times patient logged on to portal
    - what portal was used for
    - when and how often portal was used

For Northwestern patients, the same data that was requested above will be obtained through an additional EDW report, including patient medications, chronic conditions, COVID-19 diagnosis and/or results of antibody test, and healthcare utilization (ED, hospitalization, primary care appointments) as well as hypertension, diabetes and cholesterol clinical values.

#### **For Participants that complete COVID Wave 5-9.**

★ EHR Data. Medical record data will be again collected via the Electronic Health Record (EHR) from January 1, 2019 - present. EHR data will confirm comorbidities and medications. We will also extract clinical outcomes (HbA1c, diastolic and systolic blood pressure, cholesterol (LDL, HDL, total, triglycerides), GFR, COVID-

19 lab tests and results, COVID-19 diagnosis, COVID-19 vaccine type and dates, and antibody results), preventive services utilization (cancer screening, immunizations), and health services use (clinic visits (including telehealth), medical subspecialty visits, emergency department visits, hospitalizations). Lastly, we will collect patient portal usage.

**9.20 COVID-19 Survey.** We are proposing an optional sub-study to be contacted from a pool of existing studies conducted by [name] (LitCog (STU00026255), REMinD (STU00203777), COPD Multimorbidity (STU00201640), UMS Portal (STU00201639), and TAKE IT (STU00204465). Participants will be invited to participate in an optional one-time brief (5-10 minute) telephone survey to capture one additional outcome pertaining to their knowledge, attitudes, and beliefs about the COVID-19 outbreak in March 2020. This new data will be linked with participant characteristics from the parent study. They will also be asked a series of patient-reported health literacy items. Participants who complete to COVID-19 survey will receive a \$10 gift card in the mail.

Recruitment will be done by phone by trained Northwestern RAs. We will contact any who has indicated that they were willing to be contacted for future studies run by [name] on the consent form. Verbal consent will be obtained prior to completing the one time brief (5-10 minute) telephone survey.

#### Waves 2-4:

From the same pool of existing studies included in Wave 1, any participants who completed the Wave 1 COVID-19 survey will be contacted and invited to participate in up to 3 additional telephone surveys (10-30 minutes each) over the course of 4 months to continue to evaluate knowledge, attitudes, and beliefs over time about the ongoing COVID-19 pandemic. Participants who complete the follow-up interviews will receive a \$10 gift card in the mail for wave 2 and a \$15 gift card for waves 3 and 4 (per survey), for a total of up to \$40 for the follow-up activities. For wave 3 and 4, we increased the participant compensation from \$10 to \$15 due to the longer survey administered at this time point.

Recruitment will be done by phone by trained Northwestern RAs. We will invite anyone who has indicated that they were willing to be contacted for future studies run by [name] on the consent form and who completed the Wave 1 survey. Verbal consent for the follow up waves will be obtained prior to completing the Wave 2 telephone survey (initiated 2 weeks after Wave 1). Participants who consent to these follow-up activities will be re-contacted for completion of Waves 3 and 4 at 1 month and 3 months post-wave 2.

#### Waves 5-9

In March 2020, we recruited a subset of the UMS Portal cohort (n=215), and patients enrolled in four other studies (n=458; Total N=673) to form the Chicago COVID-19 Comorbidities (C3) cohort study. We initially completed four phone interviews

(described above) with them to better understand how older adults with underlying health conditions, at greater risk for COVID-19 complications, were responding and taking action (or not) to prevent infection and disease spread.

We will now continue our investigation to better understand the longer-term impact of COVID-19. From the same pool of existing studies, any participants who completed the Wave 1 COVID-19 survey will be contacted and invited to participate in up to 5 additional telephone surveys occurring every 4 months. Interviews will collect information on participants' responses to COVID-19 and changes in lifestyle behaviors, healthcare utilization, physical and mental health, access and adherence to treatment, socioeconomic circumstances and clinical outcomes. We will also collect data from the medical record and pharmacy record abstractions.

Participants who complete additional telephone surveys will receive compensation in the mail. See section 22.2 for further details.

Data from all waves of the COVID-19 telephone surveys will be captured in REDCap.

### **9.21 Post-trial investigations**

To investigate patient, healthcare provider, and/or healthcare system-level barriers to implementation, we will conduct brief online survey (n ~25-50) with clinic providers and staff to explore barriers and facilitators to implementing the various intervention strategies. The practice manager, academic manager, or clinician partner at Erie Family Health Center and Northwestern Medicine will email providers and staff that may have been involved in some aspects of the study a Redcap link to an online consent. If the provider or staff member consent and click next, they will be taken to a brief, anonymous online survey.

We will also compare the cost-effectiveness of each strategy. Specifically, we will estimate the incremental cost of interventions over the cost of usual care from the perspective of AllianceChicago, Erie Family Health Center, and Northwestern Medicine. The primary operational costs of the intervention strategies include texting related costs and the programming and maintenance costs of the Epic/GE Centricity EHR and the patient portal. We will separately track development costs of the interventions, conditional on having an EHR and portal, which are primarily comprised of software generation and other programming requirements based on programmer hours. Staff/programmer costs will be measured using tracked time spent on developing and running the intervention and converted to dollars using current wages.

## **10.0 Data and Specimen Banking**

10.1 Upon completion of all study activities, a final de-identified dataset will be created. This dataset will be stored indefinitely on the GIM server for secondary analyses.

Only authorized personnel will have access to the dataset. Data will be stored on Northwestern encrypted servers and access will be granted through the PI.

## 11.0 Data and Specimen Management

### 11.1 Analysis Plan.

#### Aim 1.

The proposed trial uses patient 1:2:2:2 randomization with random block size to achieve group comparability and balance. Stratified by clinic, each participant will be randomized to one of the four arms. The four arms are the result of a 2x2 factorial design, where SMS text reminder and portal are the two-level factors with all four arms receiving the EHR tools. We conservatively anticipate at least 80% retention for follow-up at six months. This will result in 1505 participants recruited to the study with an anticipated minimum of 1204 (172 participants in EHR arm and 344 per the other arms) available after six months, contributing to primary data analysis. Due to an NIA administrative hold, the interventions were not implemented as planned. Hence it was determined that the primary analysis would be “per-protocol” rather than intent-to-treat to assess the effect of the interventions under optimal conditions. Participants who received the initial 6 weeks of SMS messaging continuously will be considered as receiving the SMS intervention, and participants who logged on to the patient portal and completed at least one survey will be considered as receiving the patient portal.

To ensure adequate balance across treatment arms, baseline outcomes and potential confounders including socio-demographic characteristics, comorbidities, regimen complexity (i.e. # of medications, total pills taken daily), health literacy level, and language will be examined. Variables found to have clinically meaningful differences across treatment groups will be entered as covariates in the generalized linear mixed models (GLMMs) used for formal analyses as described below.

Prescription medication adherence at 6 months is the primary outcome of interest for Aim 1, with treatment knowledge regimen consolidation, and clinical outcomes being relevant to hypotheses of secondary interest. We will use generalized linear mixed-effects models (GLMMs) to test for the effects of SMS text reminder and Portal, specifying the proper link functions based on the distribution of the outcome variable. Analyses will be performed using PROC GENMOD in SAS (v.9.4). SMS text reminder and Portal (both binary) and an interaction term for SMS and Portal are the three variables included in the model to denote the intervention groups and the enhanced usual care group (H1-6). Since adherence will be assessed for each medication, 2-level GLMM will be used with medications nested in participants. We will test for differences in the outcomes between each of the groups and the enhanced usual care arm to determine benefits of SMS texting or portal use, or both by constructing contrasts.

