### 7.1 Study Duration.

1. The anticipated duration of participation will be 6 months. Patients will complete an in-person or phone baseline interview after having a regularly scheduled doctor appointment. They will then complete a 6-8 week phone interview, and a 6-month post baseline, in-person interview or phone interview (if unable to complete in person due to NU COVID-19 in-person interview restrictions).
2. We have allotted 36 months to recruit and enroll all participants.
3. We anticipate 9 additional months to finish preliminary analysis. The estimated date to complete analysis is May 2021.

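### The hold-driven per-protocol rule filters only the SMS and Portal arms, so it may break the calendar concurrency of the randomised arms, and the model has no term for period or interview mode

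*Combined protocol and SAP*

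**What the plan says.** Section 11.1, Aim 1, describes the allocation: "The proposed trial uses patient 1:2:2:2 randomization with random block size to achieve group comparability and balance". Allocation is stratified by clinic. The same paragraph then reports that "Due to an NIA administrative hold, the interventions were not implemented as planned" and continues: "Hence it was determined that the primary analysis would be “per-protocol” rather than intent-to-treat".

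Receipt is defined for the two active components. For SMS: "Participants who received the initial 6 weeks of SMS messaging continuously will be considered as receiving the SMS intervention". For the portal: "participants who logged on to the patient portal and completed at least one survey will be considered as receiving the patient portal". The four arms are described "with all four arms receiving the EHR tools", but the primary analysis sets no receipt, delivery or date criterion for enhanced usual care. The text does not say whether an active-arm patient who fails the definition is excluded or recoded as unexposed.

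The Aim 1 model has three intervention terms: SMS, Portal and their interaction. Covariates are added when an examined variable shows a clinically meaningful imbalance. The variables named are baseline outcomes and patient and regimen characteristics. Enrolment date, hold period and interview mode are not named.

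Recruitment was allotted 36 months (Section 7.1), and data collection changed within the trial. The 6-month assessment is an "in-person interview or phone interview (if unable to complete in person due to NU COVID-19 in-person interview restrictions"). By phone, patients count their own pills, with a video screenshot where possible (Section 8.2), and blood pressure is not measured (Section 9.12).

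**The concern.** Blocked randomisation within clinic gives each active patient controls enrolled at about the same time. A receipt filter on the active arms alone can remove that protection. If delivery was interrupted for a stretch of calendar time, active patients from that stretch tend to fail the definition, while controls from the same stretch remain. If non-receivers are instead recoded as unexposed, the comparison group gains hold-period patients from the active arms, which under 1:2:2:2 allocation hold six of every seven patients randomised. The imbalance would then be larger.

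This differs from the usual per-protocol worry about who opts out or ignores the portal. It could arise even if every patient complied when offered the intervention, and adjusting for patient characteristics does not address it. Any change in adherence or its measurement between periods would be partly credited to, or subtracted from, the SMS or Portal effect. The direction cannot be known in advance.

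**Working it through.** **1. The plan's own figure.** Section 11.2 gives 172 controls and 344 per other arm, 69% adherent under enhanced usual care, a 12-point difference, a 2.5% type 1 error and 80% power. Arm sizes: 1505 × 0.80 = 1204; 1204 / 7 = 172; 2 × 172 = 344.

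Power for 69% against 81%, two-sided 2.5% (z = 2.241):
- Pooled rate = (172 × 0.69 + 344 × 0.81) / 516 = 0.77.
- Null SE = √[0.77 × 0.23 × (1/172 + 1/344)] = 0.0393; critical difference = 2.241 × 0.0393 = 0.088.
- Alternative SE = √[0.69 × 0.31/172 + 0.81 × 0.19/344] = 0.0411.
- Power = Φ[(0.12 − 0.088) / 0.0411] = 78.1%.

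The detectable difference at 80% power is about 12.2 points, so the stated figure is reproduced to rounding. The plan does not state whether the test is one- or two-sided; one-sided 2.5% gives 85.2%.

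**2. Size of a calendar bias.** The documents give no hold dates, no share of patients affected and no period effect, so both inputs here are assumptions. Let f be the excess share of hold-period patients in the comparison group and d the difference in measured adherence between periods. With no true effect:

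bias = f × d

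| f | d (points) | bias (points) | type 1 error (nominal 2.5%) |
|---|---|---|---|
| 15% | 5 | 0.75 | 2.7% |
| 15% | 10 | 1.5 | 3.4% |
| 30% | 5 | 1.5 | 3.3% |
| 30% | 10 | 3.0 | 5.8% |

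The top case is 3.0 / 12 = 25% of the target difference. The error rates take 172 unfiltered controls against 344 × (1 − f) treated patients, with 69% adherence outside the hold. For f = 30%, d = 10: critical difference 0.1046, SE 0.0468, so the upper tail is 1 − Φ[(0.1046 − 0.03)/0.0468] = 5.6%; adding 0.2% from the lower tail gives 5.8%.

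Wider assumptions give a wider range: f = 10%, d = 5 gives 0.5 points, and f = 50%, d = 15 gives 7.5 points. If f = 0 or d = 0, the bias is zero.

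**3. Cost of restricting all arms to the deliverable windows.** Same power formula, with both sample sizes multiplied by (1 − share lost):

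| share lost | n (control vs active) | power for 12 points | detectable difference |
|---|---|---|---|
| 0% | 172 vs 344 | 78% | 12.2 |
| 10% | 155 vs 310 | 73% | 12.9 |
| 25% | 129 vs 258 | 65% | 14.0 |
| 50% | 86 vs 172 | 47% | 16.6 |

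These treat adherence as one proportion per patient and assume the full 12-point effect. Without a receipt filter, opt-outs and unused portals would dilute that effect and lower power further.

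**The case against.** A reader might infer that treated and control patients do come from different calendar periods with different outcome collection. The documents do not show that. They do not say when the hold began or ended, which components it stopped, or whether enrolment continued. Phone interviews are tied to COVID-19 restrictions, not to the hold, and nothing places the two in the same period. The documented mode differences concern pill count and blood pressure. The 24-hour recall that set the sample size is self-reported in either mode, so a mode effect on it is possible but not shown.

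Nor can the filter be read as driven by dates alone. For SMS, "The texts will continue daily, with the option to opt out at any time" (Section 9.14). One portal survey out of six requests, from 2 weeks to 5 months, is enough to qualify, so a patient enrolled while the portal was unavailable might still count later. There is likewise no evidence that hold-period controls missed the UMS tools; Aim 2 plans to measure receipt in all four arms. The list of potential confounders is also open-ended, so an imbalanced period variable could be added, and adjusting for baseline outcomes might absorb part of a period difference.

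All of this stands as a limit on what can be claimed. It does not dispose of the point. The plan gives the hold as its reason for leaving intention-to-treat. A hold that simply paused randomisation in every arm, with no one under treatment, would give no such reason. The text therefore implies that randomised patients were affected. An optional covariate that depends on someone noticing an imbalance is not a pre-specified safeguard.

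**Conclusion.** The concern holds as a conditional one. The rule was adopted because of the hold, applies to the SMS and Portal arms only, and may break the concurrency of the randomised arms. The plan neither rules this out nor adjusts for it. The size cannot be established from the documents. The 0.75-3 point range rests wholly on an assumed 15-30% difference in share and an assumed 5-10 point period difference, and it shows what is possible, not what happened. The bias is zero if no patient was enrolled or treated during the hold, or if adherence did not differ by period. It is likely to be larger if non-receivers are recoded as unexposed. The change should be made because the sponsor can settle the matter from dates it already holds.

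**What to change.** In the Aim 1 analysis plan:

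1. State the hold dates, which components it stopped, and whether enrolment continued.
2. State whether non-receivers are excluded or recoded as unexposed.
3. Put enrolment/follow-up period relative to the hold in the primary model, whatever imbalance is observed. It follows from the enrolment date and an external event, so it acts as a baseline variable.
4. Add 6-month interview mode as a covariate in a sensitivity analysis. Mode is fixed after randomisation, so it should not sit in the primary model.
5. From study records, define the windows in which each intervention was deliverable; for SMS, the full six weeks after baseline must fall inside the window. Compare all arms as randomised within those windows, with no receipt filter.
6. Report that comparison beside the per-protocol result and an intention-to-treat analysis of all randomised patients.

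The work is plan wording, a few derived date variables and two added analyses. The windowed comparison loses patients from every arm, including the smallest (172 controls), so its power should be stated: about 73% if 10% are lost and 65% if 25% are lost, against 78% recomputed for the stated design. Neither the period term nor the windows remove selection by opt-out or portal non-use from the per-protocol result; the as-randomised comparisons are there for that reason.
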